# **GLOSSARY OF ABBREVIATIONS**

AE	Adverse event
AIR	Allergy, Immunology and Rheumatology
BSA	Body surface area
CBC	Complete blood count
CLASI	Cutaneous Lupus Erythematosus Disease Area and Severity Index
CMP	Comprehensive metabolic panel
CTU	Clinical trials unit
DLE	Discoid lupus erythematosus
EI	Erythema index
FDA	U.S. Food and Drug Administration
IFM	Immunofluorescence microscopy
IFN	Interferon
IGA	Investigator's Global Assessment
IHC	Immunohistochemistry
IND	Investigational new drug
IRB	Institutional review board
JAK	Janus kinase
MACE	Major adverse cardiovascular event
MI	Melanin index
NRS	Numeric rating scale
PHI	Protected health information
PI	Principal investigator
RSRB	Research subjects review board
SAE	Serious adverse event
STAT	Signal transducer and activator of transcription
URMC	University of Rochester Medical Center

Version Date: 06Jun2023 Page 3 of 19

#### 1. PURPOSE OF STUDY

The primary objective of this study is to assess the potential efficacy of topical ruxolitinib for the treatment of discoid lupus erythematosus (DLE). We propose a 12-week open-label clinical trial. An exploratory objective of this study is to analyze cellular and molecular features of discoid lesions before and after treatment with topical ruxolitinib to assess 1) predictors of treatment response, and 2) treatment response to ruxolitinib.

# 2. BACKGROUND AND RATIONALE

Standard of care for patients with DLE depends on disease severity, but can include topical systemic calcineurin inhibitors, antimalarials, immunosuppressive medications. The only FDA-approved medication for DLE is hydroxychloroquine. Consequently, topical steroids and calcineurin inhibitors, as well as a number of systemic immunosuppressive medications, are also used to treat DLE. Systemic immunosuppression is used infrequently. Topical calcineurin inhibitors are generally less effective than topical steroids, but arguably may have a more favorable safety profile. Topical steroids have the potential to induce skin atrophy, an especially devastating side effect on the face, head and neck, the most commonly affected areas in DLE. Though not often used on the face to treat other skin conditions, due to the severe nature of the disease, class I superpotent topical steroids are used in DLE for short periods of time (< 2 weeks), while weaker topical steroids are generally not very effective. Antimalarials and other systemic immunosuppressive medications are effective in some DLE patients, but have significant potential side effects including retinopathy, cytopenias, liver toxicity, and increased infection risk.

Type I interferons are key inflammatory cytokines in DLE pathogenesis. These inflammatory mediators signal through the JAK-STAT pathway. Janus kinase (JAK) inhibitors, which block interferon (IFN) signaling, are a new class of therapeutics with potential efficacy in lupus. Systemic JAK inhibitors have been effective in murine models of lupus. Of particular interest is one murine study in which oral ruxolitinib, a potent JAK1/2 inhibitor, attenuates cutaneous lupus development, without much effect on systemic disease. This study suggests that ruxolitinib may be more selective in treating lupus skin disease.

Oral ruxolitinib is FDA-approved for the treatment of polycythemia vera, myelofibrosis and acute graft-versus-host disease. Topical ruxolitinib has been shown to be effective in a number of inflammatory human skin diseases including alopecia areata/universalis, vitiligo, and atopic dermatitis.  Systemic side effects have not been reported with topical use. The most common side effects from topical JAK inhibitors are mild and include local irritation, erythema, acne, or papular eruptions. In summary, we hypothesize that topical ruxolitinib may be both more effective and safer than topical steroids for the treatment of DLE.

Version Date: 06Jun2023 Page 4 of 19

#### 3. ADMINISTRATIVE ORGANIZATION

This is a single-center study in the Department of Dermatology at the University of Rochester Medical Center (URMC). [name], who is a medical dermatologist with clinical and research expertise in lupus, will be the principal investigator (PI). The study will be performed in the URMC Dermatology Clinical Trials Unit (CTU), which will provide both administrative and coordinator support for the trial. Medication management will be handled by the Investigational Drug Service of the URMC Department of Pharmacy. Safety laboratory monitoring will be done through URMC labs. Laboratory analyses of deidentified skin samples will be performed in the [name] laboratory and URMC core facilities.

# 4. STUDY DESIGN

This is a 12-week, single-center, open-label study of ruxolitinib 1.5% cream for the treatment of discoid lupus. The primary endpoint is a ≥ 2-point reduction in Investigator's Global Assessment (IGA) score at Week 12 compared to baseline. Secondary endpoints at Week 12 include the mean percentage change from baseline in the Cutaneous Lupus Erythematosus Disease Area and Severity Index (CLASI), CLASI-A (activity) and CLASI-D (damage) scores; the change in erythema and pigmentation as determined by quantitative photographic analysis; and the change in numeric rating scale (NRS) for pain and pruritus. Exploratory endpoints of skin biopsies will evaluate cellular and molecular features of discoid lesions preand post-treatment for 1) predictors of treatment response, and 2) treatment response to ruxolitinib. Quantitative and qualitative measures of the cutaneous inflammatory response, including evaluation of the immune cell infiltrate and IFN signature, will be assessed.

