# 4.1. SUBJECT POPULATION

# 4.1.1 Number of Subjects

Fifteen subjects will be consented to enroll in this study. This small sample size is justified by the rarity of this condition and the exploratory nature of the study.

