# 5. INCLUSION AND EXCLUSION CRITERIA

#### 5.1 Inclusion Criteria

# Individuals who meet all of the following criteria are eligible for enrollment as study participants:

- Ability to understand and comply with the protocol and provide informed consent.
- Speaks English.
- Age  $\geq$  18 years.
- Clinical diagnosis of discoid lupus as assessed by the PI.
- At least one active (inflamed) discoid lesion with an IGA score of  $\geq 3$  and with a diameter  $\geq 1$  cm at screening and baseline. Two lesions with equal scores will be necessary if consenting to pre-and post-treatment biopsies.
- Maximum body surface area of 20%.

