#### 8. STUDY PROCEDURES

Version Date: 06Jun2023 Page 8 of 19

This study will be a single-arm trial of ruxolitinib 1.5% cream applied twice daily for 12 weeks. Only active lesions will be treated, defined as those with erythema, scale, pain, or pruritus. Each subject will be provided with ruxolitinib cream.

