### 8.2.1 Clinical Assessments

Clinical Assessments: A detailed physical exam, past medical history and vital signs will be performed at study visit 1. A problem-focused physical exam, interval history and vital signs (heart rate, blood pressure, temperature, weight) will be performed at visits 2-7. Adverse events will be assessed at study visits 2-7.

IGA: The Investigator's Global Assessment will be performed at study visits 2-6. The IGA is an instrument to rate the severity of the subject's global disease. This IGA is comprised of a 5-point scale of disease activity ranging from 0 to 4 as follows:

- 0: "clear," no erythema or scale
- 1: "almost clear," pink erythema without scale
- 2: "mild," pink erythema with scale
- 3: "moderate," red erythema with scale
- 4: "severe," purple/violaceous or hemorrhagic/crusted erythema OR hypertrophic/ verrucous scale

CLASI: The Cutaneous Lupus Area and Severity Index will be performed at study visits 2-6. This is a validated measurement instrument designed for use in clinical trials to assess disease activity and damage in subjects with cutaneous lupus. The CLASI is comprised of two parts, CLASI-A that measures disease activity (erythema and scale), and CLASI-D that measures disease damage (pigmentation and scarring).

NRS: Subjects will maintain a symptom diary every day for 12 weeks. Specifically, subjects will rate pain and itch separately using a numeric rating scale (NRS) and the questions below. Symptom diaries will be reviewed at study visits 2-6.

On a scale of no itch (0) to worst imaginable itch (10), how itchy was the worst discoid

Version Date: 06Jun2023 Page 9 of 19

lupus lesion in the last 24 hours?

On a scale of no pain (0) to worst imaginable pain (10), how painful was the worst discoid lupus lesion in the last 24 hours?

Photography: Photographs of all discoid lesions will be taken at study visits 2-6. The Haiku app or Canto app will be used to directly load photos into the secure Epic medical record system. Images will be extracted from Epic, and analyzed as described. In brief, a melanin index (MI) and an erythema index (EI) will be generated for each lesion using Image J software analysis. The analysis uses perilesional skin to normalize the photograph. Images from serial visits will then be compared, as well as between treatment groups.

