### 14. PRIVACY AND CONFIDENTIALITY OF SUBJECTS AND RESEARCH DATA

Steps to ensure privacy and confidentiality of subjects and research data will include:

- The PI will be responsible for all aspects of this study, including privacy and confidentiality of subjects and research data.
- All study personnel will be appropriately trained in Good Clinical Practice.
- Study investigators or coordinators will meet with subjects in a private room, where they will conduct all aspects of this study that involves direct subject interaction.

Version Date: 06Jun2023 Page 15 of 19

- Subjects will not be re-contacted without prior consent. During the process of consent, subjects will be given the option to be re-contacted regarding opportunities to participate in future studies.
- All electronic and physical documentation that includes protected health information (PHI) will be stored in files and/or folders with access limited to authorized study personnel only.
- Physical files will be kept in a locked secure area of the URMC Dermatology CTU.
- Computers on which electronic PHI data is accessed will be password protected and will not be left unattended while in use.
- Passwords and system IDs will not be shared.
- Physical security of computers/files will be maintained.
- Subjects and samples will be assigned a unique code to facilitate deidentification of the data. Codes will not be generated from existing identifiers, such as initials or enrollment date.
- Only authorized study personnel will have access to data containing PHI.
- Other research personnel conducting experiments on tissue samples and analyzing data will have access to deidentified samples and data only.
- Data will be stored for at least 6 years after the completion of the study, or for at least two years following marketing approval (or, if not approved, 2 years following shipment and delivery of the investigational product is discontinued), whichever is longer.

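### No masking to visit is specified for photograph or histology readers, and nothing keeps earlier scores from the IGA/CLASI assessor, in a trial with no control arm

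*Combined protocol and SAP*

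**What the plan says.** Section 4 gives the design as a "single-center, open-label study of ruxolitinib 1.5% cream", and Section 8 states: "This study will be a single-arm trial of ruxolitinib 1.5% cream applied twice daily for 12 weeks". Section 4.1.1 sets the size: "Fifteen subjects will be consented to enroll in this study". The primary endpoint is a drop of at least 2 points, defined as a "reduction in Investigator's Global Assessment (IGA) score at Week 12 compared to baseline".

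On who reads what, and with what knowledge:

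- **IGA and CLASI.** Section 8.2.1 says "The Investigator's Global Assessment will be performed at study visits 2-6", and CLASI follows the same visits. It does not say who scores or whether earlier scores are in view.
- **Photographs.** Section 8.2.1 says "Images will be extracted from Epic, and analyzed as described". ImageJ then gives an erythema index (EI) and a melanin index (MI) per lesion, normalized to perilesional skin, and serial visits are compared. Removal of visit labels and reading order are not mentioned.
- **Tissue.** Biopsies are optional, at Weeks 0 and 12 (Section 8.2.3). Under Section 14, laboratory and analysis staff "will have access to deidentified samples and data only", using a unique code. Whether that code shows or conceals the visit is not stated.

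**The concern.** Subjects and investigators in a single-arm trial must know the treatment. A person measuring a stored image or grading a coded section need not know the time point. Selecting lesion and perilesional areas takes judgment unless it is automated, and the plan names no automatic rule. Grading histologic features and counting cells also take judgment. A reader who knows which item is Week 12 can lean toward improvement without meaning to.

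In a controlled trial with masked readers, such a lean would affect both arms and largely cancel in the comparison. Here nothing can be subtracted. The protocol's own hypothesis (Section 2) is that the cream may be more effective and safer than topical steroids, so the direction of expectation is clear. At stake are the primary endpoint (IGA), secondary endpoints (CLASI, EI, MI) and the exploratory histology, which is among the tissue comparisons that Section 17 judges at p < 0.05.

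**Working it through.** There is no power calculation or other planned figure to reproduce. The check compares the text for each measure and then works through the IGA response rule.

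**Step 1. What each reader is said to know, and what could be hidden.**

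| Measure | Endpoint level | Protocol on masking | Can the visit be hidden? |
|---|---|---|---|
| IGA | Primary | Silent | Not in person; earlier scores can be withheld |
| CLASI, CLASI-A, CLASI-D | Secondary | Silent | Same as IGA |
| EI, MI from photographs | Secondary | Silent | Largely: images are stored, exported and read later |
| Pain and itch NRS | Secondary | Self-rated daily diary | No |
| Histology grading and counts | Exploratory | Deidentified; visit not addressed | Yes, through the existing code |
| Flow cytometry, RNAseq | Exploratory | Deidentified; visit not addressed | Yes, but less open to expectation |

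The measures most easily read without the visit (photographs, histology) and those scored in person (IGA, CLASI) all lack any stated safeguard.

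**Step 2. What withholding the baseline IGA would achieve.** Section 5.1 requires "At least one active (inflamed) discoid lesion with an IGA score of" at least 3 on a 0 to 4 scale, so the qualifying score is 3 or 4. Assume that the baseline IGA used in the endpoint is also 3 or 4. Response means baseline minus Week 12 is at least 2:

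- Baseline 3: 3 − 1 = 2 responds; 3 − 2 = 1 does not. Scores 0 and 1 are responses.
- Baseline 4: 4 − 2 = 2 responds; 4 − 3 = 1 does not. Scores 0, 1 and 2 are responses.

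A Week 12 score of 0 or 1 is therefore always a response, and 3 or 4 never is. Only at a score of 2 does response depend on the baseline. An assessor without the baseline score would not know whether the deciding call is 1 versus 2 or 2 versus 3. Each grade is defined by current appearance (erythema color and scale), so scoring does not need the baseline. The gain is real but limited to that boundary.

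**Step 3. Illustration of size.** Let p be the true response rate and q the share of true non-responders scored as responders. Neither is in the documents; both are assumed. Expected observed rate = p + (1 − p) × q; expected responders = 15 × that rate.

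- p = 20%, q = 5%: 0.20 + 0.80 × 0.05 = 24%, or 3.6 of 15 instead of 3.0.
- p = 20%, q = 30%: 0.20 + 0.80 × 0.30 = 44%, or 6.6 of 15.
- p = 40%, q = 5%: 0.40 + 0.60 × 0.05 = 43%, or 6.45 of 15 instead of 6.0.
- p = 40%, q = 30%: 0.40 + 0.60 × 0.30 = 58%, or 8.7 of 15.

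For scale, 5 responders of 15 has an exact (Clopper-Pearson) 95% interval of 11.8% to 61.6%. Sampling error is wide in any case. A systematic lean is a separate problem, because it does not average out.

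**The case against.** The strongest reply is that the study is openly exploratory, with 15 subjects and limited statistical analysis, and that its open-label design is disclosed. The IGA has explicit anchors. EI and MI come from software, and flow cytometry and RNAseq are instrument-based. Section 14 already gives laboratory staff deidentified material. Section 8.2.1 only summarizes the image method; a fuller description may lie in a source not available here.

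Much of this stands, and it limits the point. A reader might infer that every efficacy reading is made knowing the visit. The documents do not support that: it is true of in-person scoring and the subject's diary, but for image and tissue readers the text is silent. A reader might also infer that image and tissue readings could be protected completely. That too goes beyond the text: a subject biopsied at Visit 2 may carry a scar (Section 9.1), which could reveal the order of later photographs. Nor is one subject in 15 (1/15 = 6.7 percentage points) an estimate of bias; it is the weight of any subject in a trial of this size.

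The reply does not remove the gap. Deidentified does not mean masked to visit. Software indices still depend on the areas chosen. An exploratory label does not make an avoidable bias useful, particularly when the readers and the coding are already planned.

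**Conclusion.** The point holds as a gap in specification with a cheap remedy. No masking to visit is stated for photograph or histology readers, and nothing keeps earlier scores from the IGA/CLASI assessor. Because there is one arm, any resulting expectation stays in the reported change.

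Its size cannot be estimated from the documents; the rates above rest on assumed values of p and q. The conclusion about the IGA boundary assumes that the endpoint's baseline score is 3 or 4, like the qualifying lesion's.

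The benefit differs by measure. It is greatest for EI/MI and histology, where the visit can be concealed. It is partial for IGA and CLASI, because the assessor still knows the visit, knows that the qualifying lesion scored at least 3, and may recall the baseline. There is none for the NRS. The remedy would therefore not make the primary endpoint masked. This is a cheap improvement, not a defect that invalidates the design.

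**What to change.** 1. **Section 8.2.1, Photography.** Before the planned EI/MI analysis, have a coordinator replace visit labels and dates on the exported images with a code that keeps lesion identity, and shuffle the order. The coordinator holds the key until lesion and perilesional areas are selected and the indices are locked. Note in the report that biopsy scars may reveal the order of some images.
2. **Section 14, sample coding.** State that the code conceals Week 0 versus Week 12 from the histology reader until gradings and counts are locked.
3. **Section 8.2.1, IGA and CLASI.** State who scores, and that scores at Visits 3 to 6 are recorded before earlier ones are viewed. Describe this as partial protection.

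No second reader is required, and treatment, visits, eligibility and sample size do not change. The cost is minor coordinator time for relabeling and key-holding. Section 3 provides for coordinator support, but the protocol gives no staff numbers, so the site should confirm that the key-holder is not also the reader.

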# 4.1. SUBJECT POPULATION

# 4.1.1 Number of Subjects

Fifteen subjects will be consented to enroll in this study. This small sample size is justified by the rarity of this condition and the exploratory nature of the study.

# 4.1.2 Gender and Age

DLE has a female predominance, but both men and women may participate. Subjects will be 18 years old or older.

# 4.1.3 Racial and Ethnic Origin

DLE affects all racial and ethnic groups, but is more frequent and more severe among African Americans than among Caucasians. Racial and ethnic origin of subjects will be monitored to reflect the diversity of our community. However, no subjects will be excluded based on race or ethnic origin.

# 4.1.4 Vulnerable Subjects

Vulnerable subjects will not be targeted, including children, pregnant women, prisoners, and decisionally impaired adults. Employees and students of the University may participate but will not be targeted or coerced.

Version Date: 06Jun2023 Page 5 of 19

#### 4.2. STUDY INTERVENTIONS

The active drug used in this trial will be ruxolitinib 1.5% cream. Ruxolitinib cream will be applied topically twice daily to areas of active disease. Ruxolitinib cream will be supplied by Incyte. Incyte's IND number for ruxolitinib is #77,101. Inventory control and storage, drug accountability, packaging and labeling, and dispensing will be managed by the URMC Investigational Drug Services. Standard topical therapies will be replaced with the study drug, and only systemic antimalarials will be continued as standard of care during this study. Details of potential risks associated with this drug is discussed in detail in **Section 9, Risks to Subjects**. Subjects are free to withdraw from the study at any time.

# 5. INCLUSION AND EXCLUSION CRITERIA

#### 5.1 Inclusion Criteria

# Individuals who meet all of the following criteria are eligible for enrollment as study participants:

- Ability to understand and comply with the protocol and provide informed consent.
- Speaks English.
- Age  $\geq$  18 years.
- Clinical diagnosis of discoid lupus as assessed by the PI.
- At least one active (inflamed) discoid lesion with an IGA score of  $\geq 3$  and with a diameter  $\geq 1$  cm at screening and baseline. Two lesions with equal scores will be necessary if consenting to pre-and post-treatment biopsies.
- Maximum body surface area of 20%.

# 5.2 Exclusion Criteria

# Individuals who meet any of these criteria are not eligible for enrollment as study participants:

- Unwillingness or inability to complete informed consent process or comply with the study protocol.
- Pregnant or breast-feeding women, or women planning to become pregnant or breastfeed during the study.
- History of coagulopathy, pulmonary embolism or deep venous thrombosis.
- History of cutaneous squamous cell carcinoma localized to the treatment area.
- Serum creatinine > 1.5 mg/dL, or alanine aminotransferase or aspartate aminotransferase  $> 1.5 \times$  upper limit of normal.
- Other dermatologic disease besides discoid lupus whose presence or treatments could complicate assessments.
- Other diseases besides dermatologic disorders whose treatment could complicate assessments. Subjects with systemic lupus erythematosus are permitted as long as they

Version Date: 06Jun2023 Page 6 of 19

- do not have unstable disease and meet all other criteria, including the exclusion criteria for systemic immunosuppressive or immunomodulating drugs (below).
- Topical treatments for discoid lupus within 2 weeks of Visit 2.
- Systemic immunosuppressive or immunomodulating drugs (e.g. oral or injectable corticosteroids, methotrexate, cyclosporine, mycophenolate mofetil, azathioprine) other than antimalarials (hydroxychloroquine, chloroquine, quinacrine) within 4 weeks or 5 half-lives of Visit 2 (whichever is longer).
- Potent systemic cytochrome P450 3A4 inhibitors or fluconazole within 2 weeks or 5 half-lives, whichever is longer, before Visit 2 (topical agents with limited systemic availability are permitted).
- Prior use of JAK inhibitors, systemic or topical, within the last 12 months.
- Ultraviolet (UV) therapy or tanning within 2 weeks prior to Visit 2 or during the duration of the treatment period.
- Any systemic or local infection that, in the opinion of the investigator, may compromise the safety of the subject or complicate assessments.
- Subjects allergic to lidocaine or with a history of keloids will not be allowed to provide an optional skin biopsy, but will be eligible for the remainder of the study.

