### 9. RISKS TO SUBJECTS

# 9.1 Risks of Participation

As with any change in treatment, there is a risk of no change or worsening of disease. All subjects in this study will have active discoid lesions. This means that their current therapeutic regimen is inadequate to control their disease. Stopping any current topical therapies may lead to worsening of disease, but continuing the same treatment regimen will not lead to clearance of disease activity.

Ruxolitinib cream: Skin-related side effects of ruxolitinib 1.5% cream are rare, but local irritation, pain, itch, erythema, acne, or papular eruptions have been observed. Systemic side effects are not expected. In the largest trial of ruxolitinib cream to date (307 patients with atopic dermatitis, 3-20% BSA), no clinically significant laboratory changes were observed. As of June 28, 2020, a total of 2350 study participants have been exposed to topical ruxolitinib, with no serious adverse events or fatal or life-threatening serious adverse reactions identified as treatment-related (Incyte, Global Investigator's Brochure v9, Aug 2020). In this study, we anticipate few effects from systemic absorption since most patients with DLE have even less cutaneous involvement than in prior studies, typically only 1-2% BSA.

While systemic side effects have not been seen with topical ruxolitinib, and the amount applied to the skin will be limited given the small area of treatment, there is a theoretical risk of side effects that have been observed with much higher oral doses. The most common side effects of oral ruxolitinib include increased risk of infection, laboratory abnormalities (cytopenias, elevated transaminases, and elevated cholesterol & triglycerides), and mild neurologic and gastrointestinal symptoms (dizziness, headache, fatigue, insomnia, diarrhea, abdominal pain). Ruxolitinib is a pregnancy Category C drug.

As with any treatment, there is a small risk of an allergic reaction, though this has not been documented for ruxolitinib cream. There is no known risk of interaction between antimalarials and the study drug ruxolitinib.

Safety monitoring and mitigating risk associated with the use of ruxolitinib cream is addressed in Section 8.2.2.

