# 13. SUBJECT WITHDRAWALS

Subjects will be notified by the study coordinator and advised in the written informed consent provided that they have the right to withdraw from the study at any time without prejudice.

If participants of the study at any point meet the exclusion criteria established in this protocol, including pregnancy, study drug will be discontinued. In addition, study drug will be discontinued for any subject who experiences any of the following (per Common Terminology Criteria for Adverse Events v5.0):

- Grade 2 event in Cardiac Disorders
- Grade 3 event in any other System Organ Class

Current research does not suggest a treatment-associated increased risk for these events. Standard treatment will proceed as necessary to ensure optimal health for the subject. In this situation, long term data will no longer be collected, and only the data collected during the duration of participation of the clinical trial will be included in the data analysis and conclusions of the study.

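### The exclusion for potent CYP3A4 inhibitors and fluconazole ends at Visit 2, so only discretionary criteria cover a subject who starts one during treatment

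*Combined protocol and SAP*

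**What the plan says.** Among the exclusions in Section 5.2 is use of "Potent systemic cytochrome P450 3A4 inhibitors or fluconazole within 2 weeks or 5 half-lives, whichever is longer, before Visit 2", with an allowance for topical agents of limited systemic availability. Sections 8.1 and 8.2.4 place Visit 2 at week 0, study day 0, and the Week 12 visit at study day 84.

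Section 13 turns the exclusion list into an on-treatment stop list: "If participants of the study at any point meet the exclusion criteria established in this protocol, including pregnancy, study drug will be discontinued". It adds stops by adverse-event grade, for Grade 2 cardiac events and for a "Grade 3 event in any other System Organ Class". It then says that "long term data will no longer be collected". It does not mention temporary interruption or restart.

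The UV and tanning criterion in Section 5.2 is worded differently. It applies "within 2 weeks prior to Visit 2 or during the duration of the treatment period". Other criteria carry no date, among them the laboratory limits ("Serum creatinine > 1.5 mg/dL, or alanine aminotransferase or aspartate aminotransferase" above 1.5 times the upper limit of normal), the infection criterion, and the two criteria on other diseases whose treatment might confound assessments.

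The protocol has no section on prohibited or concomitant medication. Section 4.2 says which lupus therapy may continue and does not mention CYP3A4 inhibitors or fluconazole. Section 9.1 discusses interaction with antimalarials only.

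**The concern.** The plan requires a washout of these drugs before the first dose and then does not name them for the period in which ruxolitinib is applied. Followed literally, it lets a subject who is prescribed a potent inhibitor or fluconazole at, say, week 5 continue the cream, although the same prescription shortly before Visit 2 would have barred entry.

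What is at stake is a minor safety matter. Section 9.1 accepts that "there is a theoretical risk of side effects that have been observed with much higher oral doses", and those oral-dose effects include cytopenias and raised transaminases. An entry washout is preventive. The protections that clearly apply on treatment (laboratory limits, grade-based stops, unscheduled visits) mostly act once a change has appeared or a concern has been raised.

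**Working it through.** **Inputs.** Treatment lasts 12 weeks (Section 8), with Visit 2 on day 0 and Week 12 on day 84, and windows of ±3 days (Section 8.2.4). The BSA limit is 20% (Section 5.1), against a typical 1-2% (Section 9.1). CBC and CMP on treatment are at weeks 4 and 12 (Section 8.2.2). There are 15 subjects (Section 4.1.1).

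**The plan's own figure.** 12 × 7 = 84 days, which matches study day 84 in the schedule. With the visit window, the period is 81 to 87 days.

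**Treatment days (1 to 84) covered by each criterion or reading.**
- CYP3A4 inhibitor or fluconazole, as written: 0 of 84. Look-backs of 14, 30, 60 and 365 days all give 0, so the drug's half-life does not matter.
- UV and tanning, as written: 84 of 84.
- CYP3A4 criterion if Section 13 is taken to move the look-back forward to each treatment day: 84 of 84. The text does not say this.
- CYP3A4 criterion with the UV-style extension: 84 of 84.

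**Can every dated criterion be moved forward?** Not uniformly. Section 5.2 also excludes use of any JAK inhibitor, topical included, in the preceding 12 months. Moved forward to a treatment day, that criterion would be met by the study drug itself. Investigators would have to decide which criteria move, and the protocol does not tell them.

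**Treated area.** 20/2 = 10 and 20/1 = 20, so the entry limit is 10 to 20 times the typical area. It equals the top of the 3-20% range in the trial that Section 9.1 cites.

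**Laboratory spacing.** 84 − 28 = 56 days between scheduled on-treatment draws (50 to 62 with both windows). A course on days 35-49 would end 84 − 49 = 35 days before the next scheduled draw. A course spanning day 28 or day 84 would be sampled while in progress.

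**Cost of an interruption,** assuming a course of 1 to 14 days (the documents give no course lengths):
- Restart when the course ends: 1/84 = 1.2% to 14/84 = 16.7% of treatment days.
- Restart after a further 14 days: 15/84 = 17.9% to 28/84 = 33.3%. This is not a ceiling, because the entry washout is the longer of 2 weeks and 5 half-lives.
- One Week 12 IGA lost: 1/15 = 6.7% of subjects.

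**The case against.** The strongest objection is that Section 13 is broader than this one criterion. Two exclusions refer to other diseases whose treatment could confound assessments, and Section 8.1 counts safety among the things assessed. An investigator could reasonably decide that a new potent inhibitor complicates safety assessment and stop the cream. The infection criterion gives another route when the drug is an antifungal. This stands. A reader might infer from the count above that the whole stop rule reaches these drugs on 0 of 84 days, and the documents do not support that. The zero belongs to the one criterion that names the drugs. The remaining routes exist but depend on judgement.

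It can also be said that the words on meeting a criterion at any point were meant to carry every exclusion forward. That is a plausible intent. The explicit extension of the UV criterion and the JAK-inhibitor example both count against it as a reading of the text. Even if it is right, Section 13 offers only discontinuation, which is out of proportion to a short fluconazole course.

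The safety case is also fair. Section 9.1 reports "307 patients with atopic dermatitis, 3-20% BSA), no clinically significant laboratory changes were observed", and no treatment-related serious adverse events among 2350 participants exposed to topical ruxolitinib by June 2020. Subjects are asked about recent systemic infections at each visit (Section 8.2.2), which may bring antifungal use to light, and unscheduled visits can include laboratory tests. All of this lowers the likely risk. It does not settle it, because the documents do not say whether any of those participants were taking an inhibitor.

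**Conclusion.** The gap is real but narrow. The only criterion that names potent CYP3A4 inhibitors and fluconazole covers none of the 84 treatment days, so Section 13 does not reach these drugs through it. Only discretionary criteria remain. This rests on the literal wording of Section 5.2 and on the absence of any other restriction on these drugs in the protocol.

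The practical risk is probably low. A reader might infer that subjects face material harm or that the efficacy result is biased. The documents support neither: they give no frequency of inhibitor use and no data on the cream with an inhibitor, so no event rate can be derived, and nothing here bears on the direction of the IGA result. The reason to act is that the plan's own precaution lapses when exposure begins, that entry is allowed up to 20% BSA, and that the repair costs little. This is a cheap improvement with a minor safety purpose.

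**What to change.** 1. In Section 5.2, add *or during the treatment period* to the CYP3A4-inhibitor and fluconazole criterion, in line with the UV criterion.
2. In Section 13, state that a short course leads to temporary interruption of study drug, and fix the restart time (end of course, or end of course plus the entry washout). State that drug is stopped permanently only if the inhibitor must continue, and that the subject stays in follow-up with the Week 12 IGA still collected.
3. Ask about these drugs in the interval history already taken at visits 2-7.

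Make the first two changes together. With the first alone, Section 13 would permanently stop the cream for a brief fluconazole course, and its sentence on ending data collection could cost that subject's Week 12 IGA, 1 of 15.

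The changes add no scheduled visits, tests or subjects. The downside is an occasional subject with days off cream: about 1-14 for an assumed course of up to 14 days with restart at its end, 15-28 if a 2-week washout is added, and more where 5 half-lives exceed 2 weeks.
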